Appendix XV – ShangRing Active Surveillance: Device Placement and Follow-up Log

ShangRing Active Surveillance: Device Placement and Follow-up Log

Appendix XVI: ShangRing Evaluation Pilot: Log of Client ShangRing Eligibility and Acceptance

ShangRing Evaluation Pilot: Log of Client ShangRing Eligibility and Acceptance

For all clients eligible on initial intake for ShangRing circumcision please fill out a line below.

To be completed during pre-MC counseling.

*If client gives a reason for declining ShangRing that can fall into these categories give the corresponding number if applicable: 1 – I don't want to try a new procedure, 2 – I heard about someone else's negative experience, 3 – I don't want to have to get an HIV test, 4 – I'm afraid it will hurt too much. If the client gives a different reason for refusing ShangRing, write the client's reason in the comment box.

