 - Total number of clients who fail to return to the circumcision site (or site indicated by service providers) for recommended follow-up (whether removal visit or AE follow-up).
 - Proportion of all men receiving VMMC services at the evaluation sites who choose ShangRing method instead of surgical circumcision.
- Document provider acceptability of ShangRing, to be measured by the following:
 - Provider perceived ease of application, ease of removal, ease of clinical management of adverse events, and preferences in comparison to conventional circumcision methods.
- Document duration of procedures, and problems encountered during procedures and post-procedure care, to be measured by the following:
 - ShangRing application time will be measured, including the overall time the client is on the procedure table, and the time required for discreet application activities: client preparation time (including application of local anesthetic and sizing), marking and device application, and clean-up time.
 - ShangRing removal time will be measured, including the overall time the client is on the procedure table, the time required for discreet removal activities, and time for post removal instructions given to the client.
- The percentage of clients determined by a clinician to be clinically healed 49-52 days post-placement of the ShangRing device (42 days post-removal), and the time at which point all clients are clinically healed.
 - Healing will be documented by evaluation staff, who will take photographs of the client's genital area during the follow-up visits.
 - Healing will meet the definition of clinical healing after VMMC, defined as:
 - "Intact epithelium (unbroken skin) covering the wound as judged by the provider on visual inspection, meaning that none of the following are present: sutures, scabbing, drainage, moisture, gaps between epithelial edges or ulceration."²⁵

Evaluation Design

Overall Design

This implementation pilot is comprised of two phases: a training phase and the main implementation pilot. During the training phase clinicians at the participating sites will be trained in the use of the ShangRing device. Upon completion of the training phase, the main implementation pilot will begin. The implementation pilot is a single arm, open label, prospective cohort evaluation.

Description of Evaluation Populations and Catchment Areas

Shinyanga, Tanzania

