The potential client's eligibility will be assessed through a medical history screening and a genital examination, which cover the inclusion criteria listed above and helps to ensure that the client is in overall good physical health. The screening and examination will be documented on evaluation forms (see Appendix VII).

Potential clients who are not eligible to participate in the evaluation will be offered standard surgical circumcision, if their reason for ineligibility does not likewise disqualify them from receiving a standard circumcision. The number and reasons for ineligibility will be recorded and included in the final evaluation report (See Appendix XII).

HIV Testing Procedures

Serological testing for HIV, which follows national standards established and approved by the Tanzanian MoHCDGEC, is a standard component of male circumcision services globally.

HIV rapid testing will be conducted after receiving written informed consent, and completion of pre-test counseling by certified personnel. Per national guidelines, any person above the age of 18, or any mature minor less than 18 years of age may give informed consent to receive HTC services. A mature minor is defined as any person below 18 years of age who is married, sexually active, or otherwise believed to be at risk for HIV infection. A young person below 18 years of age who does not meet the definition of a mature minor may receive HTC services with the written consent of a parent or legal guardian. Tanzanian national HIV guidelines for HIV counseling, testing and referral services will be followed and pre-test counseling will include an explanation of HIV infection and transmission, the meaning of test results, and risks associated with sexual behaviors. Rapid testing will be conducted using the national algorithm in Tanzania. Clients will be tested using the standard national algorithm and tests. Clients will be informed of the result of their test verbally by a counselor upon its completion.

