Client acceptability, time to return to normal activity, and clients' satisfaction with the post-circumcision cosmetic results will be summarized from data recorded on the evaluation surveys and during qualitative interviews conducted with 10% of randomly selected clients. Similarly, provider acceptability will be summarized from data recorded during qualitative interviews conducted with providers. Qualitative interviews will be digitally recorded and then transcribed by qualified staff. The recordings will be transcribed according to the local language used and then to English. The recordings will not be marked with any identifying information but with a unique identifier. Transcriptions will be reviewed electronically, using a qualitative interview analysis software such as Atlas.ti or NVivo, and analyzed for themes. The analysis of the qualitative data will be done through an inductive process where categories are identified as they emerge. Opinions generated by the 10% of clients included in the interviews will be used to tailor the messaging for future program implementation.

The percentage of men healed by day 49, and the time at which all clients are healed, will be reported from data recorded on the client CRFs. The proportion of men unsuitable for ShangRing MC will be extracted from an evaluation log maintained for the purpose of documenting the number of ineligibles and the reasons for their exclusion. Similarly, the number of men who decline ShangRing or who withdrawal will be reported as a proportion.

The photographs taken to document healing and adverse events will be used to supplement the analysis of both endpoints. Photographs will be reviewed only by evaluation project staff, and used to enhance the understanding of different adverse events and as evidence of the duration of the healing process. Photographs of all adverse events (if the client consents) will also accompany the AE reporting, to provide further clarity on these events. The photos will also be used by project staff to better educate ShangRing providers.

Long-Term Data Storage

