Appendix XII – ShangRing Case Report Form: Client Follow-Up Form

CASE REPORT FORM – ShangRing DEVICE FOLLOW-UP

Evaluation of the safety and acceptability of the ShangRing device for male circumcision in Tanzania

Site Code:

Client ID # (CID):

INSTRUCTIONS FOR THE PROPER COMPLETION OF THE CRF

Please follow the instructions below:

1. This form is to be used for ALL follow-up visits, including the removal visit, and unscheduled visits.
2. Complete a new form at each follow-up visit.
3. Use a ball-pen, DO NOT use a pencil, a marker or a fountain pen.
4. Make sure to place the separator provided under the last copy of each page so that data recorded on one page does not copy to the next.
5. Subject initials will be comprised of the first letter of the first name followed by the first two letters of the surname.
6. Fill in the form in a clear, concise and readable way. Use common medical terminology.
7. Correct wrong data by crossing out the information with a single line and writing the correct data next to it. The evaluation coordinator, or the site coordinator in the evaluation coordinator's absence, will initial and date the correction.
 - a. Example: 07/03/1969 corrected to 09/03/1969 (with initials and date of the correction)
8. Complete all the available fields, DO NOT leave empty fields.
 - a. For evaluations not performed record ND (not done).
 - b. For data not relevant to the subject or stage of evaluation record NA (not applicable).
 - c. If you do not know the data, please use the initials UNK (unknown).
 - d. Use leading zeroes if necessary (e.g.: 15 mg = 0 1 5 mg).
 - e. Make sure to complete every header on each page.
9. Please make sure to **circle the correct option** whenever it is requested.
10. Please DO NOT add wording to CRF pages unless required. For any additional comments please use the Comments Sheet at the end of the CRF modules.
11. Dates (e.g., date of birth, date of visit) will be recorded in the DD/MM/YYYY format.
 - a. Example: 19 June 2017 will be recorded as 19/06/2017
12. CID is the Client Identification Number. It comprises the initials of the site followed by the four digit enrollment date and the three digit subject consecutive number. Example: Subject number 1 in Good Hope Health Center enrolled on July 21 will be GH2107001.
13. Time will be recorded in 24:00 format.

Example: 6:15 pm will be recorded as 18:15

ShangRing Client Follow-Up Form

Client ID Number: _____

Date of visit (dd-mm-yyyy): _____

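### The log that appears to supply the proportion of men unsuitable for ShangRing opens a line only for men already eligible at intake, so that proportion will be understated

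*Protocol*

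**What the plan says.** Three parts of the protocol bear on how unsuitable men are counted.

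- **Analysis Overview:** "The proportion of men unsuitable for ShangRing MC will be extracted from an evaluation log maintained for the purpose of documenting the number of ineligibles", together with the reasons for exclusion. No appendix is named. The next sentence adds "Similarly, the number of men who decline ShangRing or who withdrawal will be reported as a proportion", without a denominator.
- **Eligibility Screening:** "The number and reasons for ineligibility will be recorded and included in the final evaluation report", with a pointer to Appendix XII. Client Exclusion Criteria makes the same promise without a pointer. The Acceptability Component also points to Appendix XII, for the survey of men who decline.
- **Appendix XVI, the eligibility and acceptance log:** "For all clients eligible on initial intake for ShangRing circumcision please fill out a line below", and "To be completed during pre-MC counseling".

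In the current numbering the form cited for ineligibility is "Appendix XII – ShangRing Case Report Form: Client Follow-Up Form", which records neither ineligibility nor refusal.

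Separately, Secondary Endpoints lists uptake among the client acceptability measures: "Proportion of all men receiving VMMC services at the evaluation sites who choose ShangRing method instead of surgical circumcision". No source form is given for it.

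**The concern.** A log meant to count ineligible men cannot do so if ineligibility at intake is the reason a man gets no line. The omission removes him from the count of unsuitable men and from the total they are divided by. The share of men seeking circumcision who cannot have the device bears directly on how far it could replace surgery, and the protocol says its results will inform Ministry policy. If a man turned away at intake leaves no entry in the log, the log cannot supply him afterwards.

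**Working it through.** **Which log is meant.** The protocol does not say, so this is an inference.

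1. Appendix XVI is the only log in the appendix list whose title refers to eligibility.
2. In-text appendix numbers are out of date. Around number XII the lag is four:
   - the active follow-up form cited as XI is now XV (Follow-Up Visits);
   - the post-operative instructions cited as XIII are now XVII (Key Post-Placement Procedure Counseling);
   - the event form cited as XIV and the severity table cited as XV are now XVIII and XIX (Adverse Event Documentation).
3. The same lag takes XII to XVI. The lag is not four everywhere: the telephone script cited as X is now XIII, and the withdrawal log cited as XXII is now XXVIII. The nearest references on both sides of XII do agree.

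**Direction of the error.** Let u1 be the share of all men who fail at intake (not logged) and u2 the share of all men who are logged and later found unsuitable.

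- True proportion unsuitable = u1 + u2
- Proportion from the log = u2 / (1 − u1)
- The log figure is the smaller when u2 < (u1 + u2)(1 − u1), that is, when 0 < u1(1 − u1 − u2). This holds whenever anyone fails at intake and not everyone is unsuitable.

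**Size.** The protocol states no proportion unsuitable to reproduce and gives neither u1 nor u2. Both are therefore assumed.

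| u1 (assumed) | u2 (assumed) | True, u1 + u2 | From the log, u2 / (1 − u1) |
|---|---|---|---|
| 5% | 0% | 5% | 0% |
| 10% | 0% | 10% | 0% |
| 20% | 0% | 20% | 0% |
| 5% | 5% | 10% | 0.05 / 0.95 = 5.3% |
| 10% | 5% | 15% | 0.05 / 0.90 = 5.6% |
| 20% | 5% | 25% | 0.05 / 0.80 = 6.3% |

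With u2 at 5%, the log figure moves by about one percentage point while the true figure goes from 10% to 25%. The log is therefore nearly blind to the part of ineligibility decided at intake.

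**The case against.** **The log may open earlier than its instruction suggests.** Its columns are not shown. It is filled in during counselling before the procedure, and one coded reason for declining is not wanting an HIV test, although Client Inclusion Criteria makes consent to that test a condition of entry. Some lines are therefore opened before all criteria have been checked, and men who fail the medical or genital examination later may already have one. This stands: 0% is the extreme case, not the expected one. It does not help men who fail the first check.

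**Other forms record ineligibility.** The screening form (Appendix VII) has a box for every criterion, and the device form (Appendix IX) asks for eligibility and a reason if not eligible. This stands in part, since some exclusions could be recovered. But neither form is the log that the Analysis Overview describes. Recruitment lists consent before confirmation of eligibility, so men turned away earlier may have no screening form. That form also makes a negative HIV result a condition of entry, while the sample size and consent sections admit HIV-positive men. The two must be reconciled before exclusions are counted from it.

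**A reader might infer that uptake is also wrong as collected.** The documents do not support this. Secondary Endpoints defines uptake over all men receiving services, which is a coherent measure of the device's share of service volume. Nothing says that it comes from Appendix XVI, and it could be taken over all clients from routine records. If, say, 75% of men were eligible and 70% of those accepted, uptake over all men would be 0.75 × 0.70 = 52.5%. The gap between 52.5% and 70% separates two different quantities under assumed inputs; it is not a bias.

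**Conclusion.** The point holds for the proportion unsuitable. Followed as written, the Appendix XVI instruction leaves out men who fail at intake and understates that proportion. The direction is certain once anyone fails at intake. The amount is not known: under assumed intake failure of 5% to 20%, and 0% to 5% of all men found unsuitable later, the log gives 0% to 6.3% against a true 5% to 25%.

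The conclusion assumes that Appendix XVI is the log meant, which is a strong inference and not a statement in the protocol, and that staff apply its instruction literally. The proportion unsuitable is a planned report item and is not among the listed endpoints. No error is found in the uptake endpoint. An added acceptance proportion would be a useful supplement, because the all-men figure alone cannot separate preference from eligibility.

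**What to change.** 1. Change the Appendix XVI instruction to one line for every male presenting for circumcision while ShangRing is being offered. Record eligible or not with the reason, offered or not, and accepted or declined with the reason.
2. Correct the Appendix XII reference in Eligibility Screening and in the Acceptability Component, and name the log in the Analysis Overview.
3. Report the proportion unsuitable as unsuitable men over all men screened.
4. Keep the uptake endpoint as defined, and report beside it the men accepting over the men eligible and offered.

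The cost is one changed instruction on an existing form, any columns it lacks for these items, a few corrected references, and slightly more log entries. The change has to be in place before recruitment to be of full use.

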Appendix XVII – ShangRing Post-Operative Care Instructions

Post-Operative Instructions

These post op care instructions will be included in pre-and post-procedure counselling for each client. For minors, the same guidance will be given to parents or guardians. A copy will also be given to clients or parents/guardians to carry home.

Wearing the ShangRing

1. It is recommended that, back at home, you rest until you have gotten used to the ShangRing being in place.
2. Do not try to remove or reposition the ShangRing yourself, and keep the penis clean and dry.
3. After the day of circumcision, you may shower or use clean bottled water to rinse the wound while the ShangRing is in place as long as you carefully dry the penis and ShangRing afterwards. Do not go swimming or wash in a bathtub.
4. Do not take part in any intensive activities (e.g. playing soccer or other strenuous manual work in construction sites or farms) to avoid dislocation of the ring. In the case of heavy sweating, be sure to clean and dry the body immediately to keep the wound from being infected, which would delay healing.
5. DO NOT HAVE SEX (INCLUDING MASTURBATION) while the ShangRing is in place. This can damage the wound, displace the device, and increase risk of infection and transmitting diseases.
6. Try not to allow your penis to dangle freely. Tightly fitted briefs are recommended in order to keep the penis from drooping downward and to keep the ring in place and avoid skin abrasion.
7. In the event that you experience mild pain (including during an erection), especially in the first few days after the circumcision, over-the-counter pain medications such as paracetamol (acetaminophen), naproxen or ibuprofen can be used for pain relief. If the pain is excessive, contact your health care provider for further advice. Urinating may help to quickly end an erection.
8. Keep the circumcised area clean and dry. This will promote proper healing. When urinating, use a piece of toilet paper or cloth to prevent urine from seeping into the circumcision area, possibly resulting in infection.
9. Do not apply ointment or cream on or around the circumcised area. Also you should not apply traditional remedies or any other substances (e.g. herbs, soil, cow dung). This may slow the healing process, and can also increase risk for infection, including tetanus, which can be fatal.
10. You may experience slight swelling around the ShangRing. This is normal as long as it does not cause you too much discomfort. Wearing tightly fitted briefs to keep the penis facing up should help prevent swelling.

Post-operative Care instructions

11. Seven days after your circumcision, return to the clinic to have the ShangRing removed. Do not try to remove or reposition the ShangRing yourself. This can cause serious bleeding or infection. If the device does come off or gets moved, contact the clinic immediately

After Removal of the ShangRing

1. Keep the bandage clean and dry and remove the bandage before going to sleep. In the event that the bandage does get wet, replace the bandage immediately. Replace the bandage in the morning after removal and repeat for one additional day. Starting on the third day, you can wash the penis and the wound area normally and leave the bandage off.
2. Do not apply ointment or cream on or around the wound. Also you should not apply traditional remedies or any other substances (e.g. herbs, soil, cow dung). This may slow the healing process, and can also increase risk for infection, including tetanus, which can be fatal.
3. DO NOT HAVE SEX (INCLUDING MASTURBATION) within the 6 weeks after your circumcision or until the wound has healed completely. Early sex can damage the wound and increase risks of disease transmission. If you absolutely cannot avoid having sex before 6 weeks, masturbation is safest, and sex with condoms is safer than unprotected sex. After six weeks, you should use condoms to protect the circumcision wound (as well as to reduce the transmission of HIV and other infections) for three months, even after it appears completely healed.
4. Expect the complete healing of the wound may take 3 to 4 weeks, or longer.

When to come to clinic or call your doctor

While wearing the ShangRing or after removal, contact your health care provider at cell phone #:

_____ or _____, or visit the clinic:

1. If you notice bleeding from around the ShangRing or from the wound after the ShangRing surgery or the ShangRing removal.
2. If you experience difficulty passing urine.
3. If you experience seriously painful swelling, increasing redness, bruising, elevated temperature around the wound, fever, or the discharge/appearance of pus.
4. If there is severe swelling around the ShangRing, or around the area in which the ShangRing was placed which causes you discomfort.
5. If you experience excessive pain (including during an erection) while the ring is still in place.
6. If the ShangRing is damaged or comes off accidentally (partially or completely).
7. If you have any other inquiries or concerns.

